#### **Additional hepatic data collection in study participants who have abnormal liver test results during the study**

Additional hepatic safety data collection in hepatic safety CRF should be performed in study participants who meet 1 or more of the following conditions:

- Elevation of serum ALT to  $\geq 5 \times$  ULN on 2 or more consecutive blood tests (if baseline ALT  $< 1.5 \times$  ULN)
  - In participants with baseline ALT  $\geq 1.5 \times$  ULN, the threshold is ALT  $\geq 3 \times$  baseline on 2 or more consecutive tests
- Elevated serum TBL to  $\geq 2 \times$  ULN (if baseline TBL  $< 1.5 \times$  ULN) (except for cases of known Gilbert's syndrome)
  - In participants with baseline TBL  $\geq 1.5 \times$  ULN, the threshold should be TBL  $\geq 2 \times$  baseline
- Elevation of serum ALP to  $\geq 2 \times$  ULN on 2 or more consecutive blood tests (if baseline ALP  $< 1.5 \times$  ULN)
  - In participants with baseline ALP  $\geq 1.5 \times$  ULN, the threshold is ALP  $\geq 2 \times$  baseline on 2 or more consecutive blood tests
- Hepatic event considered to be an SAE
- Discontinuation of study intervention due to a hepatic event.

Note: The interval between the 2 consecutive blood tests should be at least 2 days.

### **8.3. Adverse Events, Serious Adverse Events, and Product Complaints**

The definitions of the following events can be found in Appendix 3 (Section 10.3):

- AEs
- SAEs
- Product complaints (PCs)

These events will be reported by the participant (or, when appropriate, by a caregiver, surrogate, or the participant's legally authorized representative).

The investigator and any qualified designees are responsible for detecting, documenting, and recording events that meet these definitions and remain responsible for following up events that are serious, considered related to the study intervention or study procedures, or that caused the participant to discontinue the study intervention or study (see Section 7).

Care will be taken not to introduce bias when detecting events. Open-ended and non-leading verbal questioning of the participant is the preferred method to inquire about event occurrences.

Investigators are responsible for monitoring the safety of participants who have entered this study and for alerting Lilly or its designee to any event that seems unusual, even if this event may be considered an unanticipated benefit to the participant.

The investigator is responsible for the appropriate medical care of participants during the study.

After the initial report, the investigator is required to proactively follow each participant at subsequent visits/contacts. All SAEs will be followed until resolution, stabilization, the event is otherwise explained, or the participant is lost to follow-up (as defined in Section 7.3). For PCs, the investigator is responsible for ensuring that follow-up includes any supplemental investigations as indicated to elucidate the nature and/or causality. Further information on follow-up procedures is provided in Appendix 3 (Section 10.3).

### 8.3.1. Timing and Mechanism for Collecting Events

This table describes the timing, deadlines, and mechanism for collecting events.

Event	Collection Start	Collection Stop	Timing for Reporting to Sponsor or Designee	Mechanism for Reporting	Back-up Method of Reporting
Adverse Event					
AE	Signing of the informed consent form (ICF)	Participation in study has ended	As soon as possible upon site awareness	AE CRF	N/A
Serious Adverse Event					
SAE and SAE updates – prior to start of study intervention and deemed reasonably possibly related with study procedures	Signing of the ICF	Start of intervention	Within 24 hours of awareness	SAE paper form	SAE paper form
SAE# and SAE updates – after start of study intervention	Start of intervention	Participation in study has ended	Within 24 hours of awareness	SAE paper form	SAE paper form
SAE* – after participant's study participation has ended and the investigator becomes aware	After participant's study participation has ended	N/A	Promptly	SAE paper form	N/A

Event	Collection Start	Collection Stop	Timing for Reporting to Sponsor or Designee	Mechanism for Reporting	Back-up Method of Reporting
Pregnancy					
Pregnancy in female partners of male participants	After the start of study intervention	1 week after the last dose	Within 24 hours (see Section 8.3.2)	Pregnancy paper form	Pregnancy paper form
Product Complaints					
PC associated with an SAE or might have led to an SAE	Start of study intervention	End of study intervention	Within 24 hours of awareness	PC form	N/A
PC not associated with an SAE	Start of study intervention	End of study intervention	Within 1 business day of awareness	PC form	N/A
Updated PC information	—	—	As soon as possible upon site awareness	Originally PC form with all changes signed and dated by the investigator	N/A
PC (if investigator becomes aware)	Participation in study has ended	N/A	Promptly	PC form	

\* SAEs should not be reported unless the investigator deems them to be possibly related to study treatment or study participation.

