### 8.3.2. Pregnancy

#### Collection of pregnancy information

##### *Male participants with partners who become pregnant*

- The investigator will attempt to collect pregnancy information on any male participant's female partner who becomes pregnant while the male participant is in this study. This applies only to male participants who receive study intervention.
- After learning of a pregnancy in the female partner of a study participant, the investigator will obtain a consent to release information from the pregnant female partner directly, and within 24 hours after obtaining this consent will record pregnancy information on the appropriate form and submit it to the sponsor.
- The female partner will also be followed to determine the outcome of the pregnancy. Information on the status of the mother and child will be forwarded to the sponsor.

Generally, the follow-up will be no longer than 6 to 8 weeks following the estimated delivery date. Any termination of the pregnancy will be reported regardless of gestational age, fetal status (presence or absence of anomalies), or indication for the procedure.

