#### 10.4.2.2. Male Participants

Male participants, regardless of their fertility status, with partners who are non-pregnant females of childbearing potential, must agree to either

1. remain abstinent (if this is their preferred and usual lifestyle), or
2. use condoms with spermicide plus 1 additional highly effective contraception method (see Section 10.4.3), during intercourse.

They must agree to adhere to these restrictions for the duration of the study and for 6 months after the last dose of study intervention.

Male participants with pregnant partners must agree to use condoms with spermicide during intercourse.

All male participants should refrain from sperm donation for the duration of the study and for 6 months after the last dose of study intervention.

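### Partner-pregnancy collection stops 1 week after the last dose although men must avoid conception for 6 months, so conceptions in most of that period are not collected (minor safety-collection gap)

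*Protocol*

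**What the plan says.** The timing table in Protocol Section 8.3.1 has one pregnancy row. Collection begins after the start of study intervention, stops "1 week after the last dose", and refers the reader to Section 8.3.2. That section has the investigator try to collect information on any "female partner who becomes pregnant while the male participant is in this study", for men who received study intervention.

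The precaution period is in Section 10.4.2.2. Of men whose partners are non-pregnant and of childbearing potential, it says: "They must agree to adhere to these restrictions for the duration of the study and for 6 months after the last dose of study intervention". For all men it adds: "All male participants should refrain from sperm donation for the duration of the study and for 6 months after the last dose" of study intervention.

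The 8.3.1 table also has rows, with no stop date, for SAEs and product complaints that the investigator learns of once "study participation has ended" or its equivalent. Pregnancy has no such row. A footnote limits the late-SAE row: "SAEs should not be reported unless the investigator deems them to be possibly related to study treatment or study participation". Section 10.3.2 classes abnormal pregnancy outcomes as SAEs.

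**The concern.** The protocol treats the 6 months after the last dose as a time when men should not father a child, yet it asks for pregnancy information for only the first week. No passage explains the difference. If the plan is followed exactly, a contraception failure in month 2 or month 5 is not recorded, its outcome is not followed, and the sponsor learns of it only by chance or through a related abnormal outcome. What would be lost is reproductive-safety information on an investigational drug.

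**Working it through.** This is day counting; no power or error-rate calculation is involved.

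**Inputs**
- Last dose: Day 17 (Section 4.1, pirtobrutinib alone on Days 14 to 17).
- Residence in the unit: Day -1 to discharge on Day 18 (Section 4.1).
- Collection stop: last dose + 7 days (Section 8.3.1).
- Follow-up: 7 ± 2 days after the last dose (Section 4.1).
- Precaution period: 6 months after the last dose (Section 10.4.2.2). The protocol does not give this in days, so I take 168 days (six 4-week months) to 184 days (the longest six calendar months).
- Half-lives: pirtobrutinib about 20 h (Section 2.2), rosuvastatin 19 h (Section 4.2).

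**Where collection stops**
- Completer: 17 + 7 = Day 24, which is 24 − 18 = 6 days after discharge.
- Early discontinuation brings the stop forward. A last dose on Day 6 gives 6 + 7 = Day 13.
- Section 8.3.2 is tied to being in the study. Participation ends at follow-up, between 17 + 5 = Day 22 and 17 + 9 = Day 26, so the two sections agree to within 2 days.

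**What is left uncollected**

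| 6 months taken as | Precautions end | Days after collection stops | Share not covered |
|---|---|---|---|
| 168 days | 17 + 168 = Day 185 | 168 − 7 = 161 | 161/168 = 95.8% |
| 184 days | 17 + 184 = Day 201 | 184 − 7 = 177 | 177/184 = 96.2% |

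If the Section 8.3.2 limit is used instead, each day count moves by at most 2.

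**Drug left in plasma on Day 24** (assuming mono-exponential decline from the last dose)
- Pirtobrutinib: 7 × 24 = 168 h; 168/20 = 8.4 half-lives; 2^−8.4 = 0.30%.
- Rosuvastatin, last given on Day 13: 11 × 24 = 264 h; 264/19 = 13.9 half-lives; 2^−13.9 = 0.007%.

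**Other routes.** The late-SAE row could take an abnormal outcome, reading Section 10.3.2 as covering a partner's pregnancy. It depends on the investigator hearing of the event and judging it possibly related. A normal outcome has no route.

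**The case against.** The strongest reply is that nothing here conflicts. Sections 8.3.1 and 8.3.2 agree with each other and with the end of follow-up. Section 10.4.2.2 does a different job: it prevents conception rather than collecting data, so the two windows need not match. With about 0.3% of pirtobrutinib left at Day 24, one week can be defended on plasma exposure, and 6 months may simply be cautious. Nothing in the documents shows that data are needed to month 6.

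Much of this stands. The documents do not prove that the longer window is the right one. But plasma washout does not explain a 6-month restriction either, and the protocol chose that period itself. Having done so, it should either collect the failures or say why it does not.

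A reader might also infer that Day 24 is a deadline for reporting, so that a pregnancy conceived just after discharge but recognised later would be lost. The documents do not support that. Section 8.3.2, which the table row cites, is keyed to when the partner becomes pregnant and sets no deadline for the site to learn of it. It also expects activity long after Day 24: "Generally, the follow-up will be no longer than 6 to 8 weeks following the estimated delivery date". A conception in the days between discharge and the end of participation is therefore within scope whenever it comes to light. The gap concerns conceptions after participation ends.

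**Conclusion.** The point holds as a minor mismatch between the collection window and the protocol's own precaution period. For completers, conceptions in about 161 to 177 of the 168 to 184 post-dose days are not collected, apart from abnormal outcomes that reach the late-SAE row. The range reflects only how a month is counted.

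The 96% is a share of days, not a risk. It would be wrong to infer that many exposed pregnancies are missed: about 36 participants are enrolled, the restricted men must abstain or use condoms with spermicide plus a highly effective method, and plasma drug is nearly gone when collection stops. The PK endpoints, the participant TEAE/SAE endpoint and the sample size are unaffected. The consent form was not available to this review and may already ask men to report later pregnancies.

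**What to change.** - **Section 8.3.1:** set the pregnancy Collection Stop to 6 months after the last dose, defined by date of conception, and state that such a pregnancy is reportable whenever the site becomes aware of it. The table already uses this device for late SAEs and product complaints.
- **Section 8.3.2:** replace the in-study limit with conception from first dose to 6 months after the last dose.
- **At discharge:** ask men to telephone the site if a partner becomes pregnant in that period, with matching consent text if it is not already there.

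If the sponsor prefers to keep one week, a sentence giving the reason would remove the unexplained difference but not collect the data.

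The cost is wording, with no added visits. A passive reporting channel stays open about 25 weeks longer (about 175 days with calendar months; 175/7 = 25). Any pregnancy reported needs the partner's own consent and outcome follow-up past the end of study defined in Section 4.4.

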### 8.3.2. Pregnancy

#### Collection of pregnancy information

##### *Male participants with partners who become pregnant*

- The investigator will attempt to collect pregnancy information on any male participant's female partner who becomes pregnant while the male participant is in this study. This applies only to male participants who receive study intervention.
- After learning of a pregnancy in the female partner of a study participant, the investigator will obtain a consent to release information from the pregnant female partner directly, and within 24 hours after obtaining this consent will record pregnancy information on the appropriate form and submit it to the sponsor.
- The female partner will also be followed to determine the outcome of the pregnancy. Information on the status of the mother and child will be forwarded to the sponsor.

Generally, the follow-up will be no longer than 6 to 8 weeks following the estimated delivery date. Any termination of the pregnancy will be reported regardless of gestational age, fetal status (presence or absence of anomalies), or indication for the procedure.

## **8.4. Pharmacokinetics**

Venous blood samples of approximately 2 mL will be collected for measurement of plasma concentrations of rosuvastatin and pirtobrutinib as specified in the SoA (Section 1.3).

A maximum of 3 samples may be collected at additional time points during the study if warranted and agreed upon between the investigator and the sponsor.

Instructions for the collection and handling of biological samples will be provided by the sponsor. The actual date and time (24-hour clock time) of each sample will be recorded.

### **8.4.1. Bioanalysis**

Samples will be analyzed at a laboratory approved by the sponsor and stored at a facility designated by the sponsor.

Concentrations of rosuvastatin and pirtobrutinib will be assayed using a validated liquid chromatography tandem mass spectrometry (LC-MS/MS) method.

Bioanalytical samples collected to measure investigational product concentrations will be retained for a maximum of 1 year following last participant visit for the study. During this time, samples remaining after the bioanalyses may be used for exploratory analyses such as metabolism and/or protein binding work.

## **8.5. Pharmacodynamics**

Pharmacodynamic parameters are not evaluated in this study.

## **8.6. Genetics**

A blood sample will be collected at screening to determine genetic polymorphisms for participants to meet eligibility criteria prior to enrollment (Section 5.2 and Section 5.2.1).

A separate blood sample will be collected for storage for potential pharmacogenetic analysis as specified in the SoA (Section 1.3). See Appendix 5 (Section 10.5) for information regarding genetic research.

## **8.7. Biomarkers**

Biomarkers are not evaluated in this study.

## **8.8. Immunogenicity Assessments**

Immunogenicity is not evaluated in this study.

## **8.9. Health Economics**

This section is not applicable for this study.

## 9. Statistical Considerations

The statistical analysis plan (SAP) will be finalized prior to first participant first visit, and it will include a more technical and detailed description of the statistical analyses described in this section. This section is a summary of the planned statistical analyses.

### 9.1. Statistical Hypotheses

The primary objective variables will be evaluated to assess the potential DDI. No significant DDI for rosuvastatin will be concluded if the respective 90% confidence interval for area under the concentration versus time curve from time zero to infinity (AUC[0-∞]) and maximum observed drug concentration (Cmax) is completely contained within the no-effect boundaries (0.80, 1.25).

### 9.2. Analyses Sets

The following populations are defined:

Population	Description
Entered	All participants who sign the ICF.
Enrolled	All participants assigned to study intervention, regardless of whether they take any doses.
Safety	All participants who receive at least 1 dose of rosuvastatin. Participants will be analyzed according to the intervention they actually received.
Pharmacokinetic	All participants who receive at least 1 dose of rosuvastatin and have evaluable PK data.

#### 9.2.1. Study Participant Disposition

All participants who discontinue from the study will be identified and the extent of their participation in the study will be reported. If known, a reason for their discontinuation will be given.

A detailed description of participant disposition will be provided at the end of the study.

#### 9.2.2. Study Participant Characteristics

The participant's age, sex, weight, height, and other demographic characteristics will be recorded.

## 9.3. Statistical Analyses

Statistical analysis of this study will be the responsibility of the sponsor or its designee.

Any change to the data analysis methods described in the protocol will require an amendment only if it changes a principal feature of the protocol. Any other change to the data analysis methods described in the protocol, and the justification for making the change, will be described

in the SAP and the clinical study report. Additional exploratory analyses of the data will be conducted as deemed appropriate.

Study results may be pooled with the results of other studies for safety and population PK analysis purposes to avoid issues with post-hoc analyses and incomplete disclosures of analyses.

### **9.3.1. Pharmacokinetic Analyses**

All PK analyses will be made using the Pharmacokinetic Population.

#### **9.3.1.1. Pharmacokinetic Parameter Estimation**

PK parameter estimates for rosuvastatin will be calculated by standard noncompartmental methods of analysis.

The primary parameters for analysis will be  $C_{max}$  and  $AUC(0-\infty)$  of rosuvastatin. Other noncompartmental parameters, such as  $t_{max}$ ,  $t_{1/2}$ , apparent clearance, and apparent volume of distribution may be reported.

Blood samples collected for the PK of pirtobrutinib alone will be used to determine plasma concentration only, to ensure sufficient exposure.

#### **9.3.1.2. Pharmacokinetic Statistical Inference**

PK parameters will be evaluated to estimate drug interaction for rosuvastatin with single (Day 6) and multiple (Day 13) doses of pirtobrutinib. A subject may be excluded from the PK summary statistics and statistical analysis if the subject has an AE of vomiting that occurs at or before 2 times median  $t_{max}$ .

Log-transformed  $C_{max}$  and  $AUC(0-\infty)$  parameters for rosuvastatin will be evaluated in a linear mixed-effects model with a fixed effect for treatment, and a random effect for participant. The treatment differences will be back transformed to present the ratios of geometric means and the corresponding 90% confidence interval.

The  $t_{max}$  will be analyzed using a Wilcoxon signed rank test. Estimates of the median difference based on the observed medians, 90% confidence intervals, and p-values from the Wilcoxon test will be calculated.

### **9.3.2. Safety Analyses**

All safety analyses will be made using the Safety Population.

#### **9.3.2.1. Clinical Evaluation of Safety**

All investigational product and protocol procedure AEs will be listed, and if the frequency of events allows, safety data will be summarized using descriptive methodology.

The incidence of AEs for each treatment will be presented by severity and by association with investigational product as perceived by the investigator. AEs reported to occur prior to enrollment will be distinguished from those reported as new or increased in severity during the study. Each AE will be classified by the most suitable term from the medical regulatory dictionary. AEs by day of onset will be presented.

The number of SAEs will be reported.

#### **9.3.2.2. Statistical Evaluation of Safety**

Safety parameters that will be assessed include safety laboratory parameters and vital signs. The parameters will be listed, and summarized using standard descriptive statistics. Additional analysis will be performed if warranted upon review of the data.

#### **9.4. Interim Analysis**

No interim analyses are planned for this study. If an unplanned interim analysis is deemed necessary for reasons other than a safety concern, the protocol must be amended.

#### **9.5. Sample Size Determination**

## **10. Supporting Documentation and Operational Considerations**

### **10.1. Appendix 1: Regulatory, Ethical, and Study Oversight Considerations**

#### **10.1.1. Regulatory and Ethical Considerations**

This study will be conducted in accordance with the protocol and with the following:

- Consensus ethical principles derived from international guidelines including the Declaration of Helsinki and Council for International Organizations of Medical Sciences International Ethical Guidelines
- Applicable ICH Good Clinical Practice (GCP) Guidelines
- Applicable laws and regulations.

The protocol, protocol amendments, ICF, Investigator's Brochure (IB), and other relevant documents (for example, advertisements) must be submitted to an institutional review board (IRB)/independent ethics committee (IEC) by the investigator and reviewed and approved by the IRB/IEC before the study is initiated.

Any amendments to the protocol will require IRB/IEC approval before implementation of changes made to the study design, except for changes necessary to eliminate an immediate hazard to study participants.

Protocols and any substantial amendments to the protocol will require health authority approval prior to initiation except for changes necessary to eliminate an immediate hazard to study participants.

The investigator will be responsible for the following:

- Providing written summaries of the status of the study to the IRB/IEC annually or more frequently in accordance with the requirements, policies, and procedures established by the IRB/IEC
- Notifying the IRB/IEC of SAEs or other significant safety findings as required by IRB/IEC procedures
- Providing oversight of study conduct for participants under their responsibility and adherence to requirements of 21 Code of Federal Regulations (CFR), ICH guidelines, the IRB/IEC, European regulation 536/2014 for clinical studies (if applicable), and all other applicable local regulations.

Investigator sites are compensated for participation in the study as detailed in the clinical trial agreement.

